##### 3.6.2.2 *Bacterial Antibiotic Resistance*

Patient incidence of antibiotic resistance will be summarized across all *E. coli* isolates. All patient antibiotic resistance data will be listed, including MIC values and interpretations.

##### 3.6.2.3 *Bacterial Metagenomics Analysis*

The metagenomics data will be available following the study’s completion, and this analysis will be described in a separate analysis plan.

#### 3.6.3 *Microbiological Isolates*

Any persisting microbiological isolates identified will have all related data listed, including bacteriophage host range and antibiotic resistance patterns. Genetic sequencing of isolates will be included in the separate metagenomics analysis.

### 3.7 Safety Assessment

Safety data will be summarized by actual treatment received (and in total for selected analyses) based on the Safety Population.

### 3.7.1 Adverse Events (AEs)

AEs will be captured from the date of informed consent through study completion. All AEs will be coded to system organ class and preferred term using MedDRA version 22.0.

Treatment-emergent adverse events (TEAEs) are defined as AEs that start after the first dose of study drug.

Adverse events of special interest include signs and symptoms of a urinary tract infection (UTI) and local vesicular reaction.

An overview of AEs will be provided including counts and percentages of patients (and event counts) with the following:

- Any TEAEs (overall and by maximum severity)
- Any study drug related TEAEs (overall and by maximum severity)
- Any TEAEs of special interest (overall and by maximum severity)
- Any serious AEs (SAEs)
- Any treatment-emergent serious AEs (TESEAEs)
- Any TEAEs leading to discontinuation of study drug
- Any TEAEs leading to discontinuation of study
- Any AEs leading to death

Counts and percentages of patients (and event counts) will also be presented by system organ class and preferred term for each of the categories in the overview.

All AE data will be listed. Listings will be presented specifically for SAEs and TEAEs leading to discontinuation of study drug, as well as TEAEs of special interest.

### 3.7.2 Clinical Laboratory Tests

Blood and urine samples for clinical laboratory tests will be collected at timepoints specified in the SoA of the protocol and processed by a central laboratory. A list of laboratory tests to be performed is included in Appendix A.

#### 3.7.2.1 Hematology, Chemistry, Coagulation, Lipids, and Urinalysis

Values and changes from baseline will be presented at each scheduled visit and baseline by laboratory test. The incidence of abnormalities (as defined by normal ranges) prior to the first dose of study drug and after the first dose of study drug will be summarized with counts and percentages of patients. Data will be listed.

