### 2.3 Study Endpoints

#### 2.3.1 *Primary Endpoints*

The primary endpoints involve summarizing the safety and tolerability of AEs and lab parameters, as well as the PK parameters of LBP-EC01. The PK parameters will be assessed as a combined set of all crPhages included in LBP-EC01 in both urine and blood.

The blood PK parameters will include the following assessments of LBP-EC01:

- Maximum concentration ( $C_{max}$ )
- Time to  $C_{max}$  ( $T_{max}$ )
- Area under the concentration versus time curve (AUC) from time 0 to the last measurable concentration ( $AUC_{0-t}$ )

Other PK variables may be calculated as appropriate for the observed data.

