## 3 STATISTICAL METHODOLOGY

### 3.1 General Considerations

#### 3.1.1 *Definition of Baseline*

Baseline is defined as the last measurement prior to the first dose of study drug unless otherwise specified.

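### The laboratory abnormality table (SAP 3.7.2.1) ignores baseline status, so it cannot separate new from pre-existing abnormalities and it dilutes the drug-placebo contrast

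*SAP*

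**What the plan says.** SAP Section 3.7.2.1 covers hematology, chemistry, coagulation, lipids and urinalysis. It fixes three outputs:

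- A by-visit summary: "Values and changes from baseline will be presented at each scheduled visit and baseline by laboratory test".
- A count of abnormalities, with the normal range as the criterion and the patient as the unit. Their incidence "prior to the first dose of study drug and after the first dose of study drug will be summarized with counts and percentages".
- Listings of the laboratory results.

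The abnormality count has no condition on baseline status, no high/low direction, no breakdown by visit and no shift table.

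Other sections that bear on it:

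- Section 3.1.1 supplies a baseline: "Baseline is defined as the last measurement prior to the first dose of study drug unless otherwise specified". Section 3.7.2.1 uses it for changes but not for the abnormality count.
- Section 2.3.1 makes laboratory data part of the primary endpoints: "The primary endpoints involve summarizing the safety and tolerability of AEs and lab parameters".
- Section 3.1.5 states that no formal hypothesis is tested.
- Section 3.7 provides the comparison with concurrent placebo: "Safety data will be summarized by actual treatment received (and in total for selected analyses) based on the Safety Population".
- Section 3.7.1 defines treatment-emergent adverse events. There is no matching definition for laboratory abnormalities.
- Section 3.7.3 counts above-range immunoglobulins at each timepoint, so a finer tabulation is used elsewhere in the same plan.

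**The concern.** The table gives two marginal percentages per arm: patients abnormal before dosing and patients abnormal after it. The safety question is how many patients who were not abnormal became so on treatment, and two margins do not answer that. A patient with an unchanged pre-existing abnormality adds to the post-dose count. Because direction is not recorded, a patient who was low before and high after looks the same as one who never changed.

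This is a first-in-human study with no hypothesis test, so the descriptive tables are the primary safety result. The weakness is likely to be greatest in urinalysis. Section 2.2.1 describes patients with *E. coli* colonization of the urinary tract, many of them catheterized, and names hematuria as a sign of a local vesicular reaction. Section 3.7.1 makes that reaction an adverse event of special interest. Appendix A includes dipstick blood and white cells. If many patients already have abnormal urine at entry, the table is least informative for the organ into which the drug is instilled.

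**Working it through.** The plan states no abnormality rate, effect size or power, so there is no figure of its own to reproduce. The check is algebra with assumed rates.

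**Inputs**

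- Arm sizes: 36 patients at 2:1 (Section 2.2.4), so 36 × 2/3 = 24 on LBP-EC01 and 36 × 1/3 = 12 on placebo.
- q, the share abnormal at baseline, equal in both arms: assumed 5%, 30%, 60% or 90%.
- r, the rate of new abnormality among patients normal at baseline: assumed 30% on drug and 5% on placebo, a true difference of 25 points.
- Patients abnormal at baseline stay abnormal: assumed.

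**Step 1: dilution of the between-arm contrast**

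Post-dose percentage in an arm = q + (1 − q) × r.

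Difference between arms = (1 − q) × (0.30 − 0.05).

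| q | Drug, post-dose | Placebo, post-dose | Difference (points) | Expected normal at baseline, drug / placebo |
|---|---|---|---|---|
| 5% | 33.5% | 9.75% | 23.75 | 22.8 / 11.4 |
| 30% | 51.0% | 33.5% | 17.5 | 16.8 / 8.4 |
| 60% | 72.0% | 62.0% | 10.0 | 9.6 / 4.8 |
| 90% | 93.0% | 90.5% | 2.5 | 2.4 / 1.2 |

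Example at q = 60%: drug 0.60 + 0.40 × 0.30 = 0.72; placebo 0.60 + 0.40 × 0.05 = 0.62.

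One patient is 1/24 = 4.2 points on drug and 1/12 = 8.3 points on placebo. A 2.5-point difference is therefore less than one patient in either arm.

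**Step 2: what the two margins leave open**

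Drop the assumption that abnormal patients stay abnormal. Let b be the share abnormal before and a the share abnormal after. The newly abnormal share of the arm can lie anywhere from max(0, a − b) to min(a, 1 − b).

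- Drug at q = 60% (b = 60%, a = 72%): 12% to 40% of the arm. Among the 40% normal at baseline, that is 12/40 = 30% up to 40/40 = 100%.
- Placebo at q = 60% (b = 60%, a = 62%): 2% to 40% of the arm. Among those normal at baseline, that is 2/40 = 5% up to 100%.

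The same printed percentages fit very different numbers of new abnormalities.

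**Step 3: the baseline-normal denominator**

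Restricting the count to patients normal at baseline gives 30% versus 5%, a 25-point difference, at every q. It does not restore precision: at q = 90% only about 2.4 and 1.2 patients are expected to contribute.

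**The case against.** The case on the other side has five parts.

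1. **Placebo is concurrent.** Safety is shown by treatment received, so both arms carry pre-existing abnormalities. That stands against a claim of bias between arms. It does not answer dilution, because the contrast itself is what shrinks in Step 1.

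2. **The pre-dose percentage is in the table.** A reader could compute (a − b)/(1 − b) and recover 30% and 5%. This works only if every abnormal patient stays abnormal, which the table cannot confirm. If some abnormalities resolve after dosing, resolved and new cases offset each other in the margins.

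3. **Other outputs exist.** By-visit changes come with median, minimum and maximum (Section 3.1.4), and all data are listed for 36 patients. New abnormalities are therefore not hidden from every output, and it would be wrong to say so. But none of these gives an incidence of new abnormalities by arm; the reader would have to build it by hand from the listings.

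4. **The urinalysis rate is not documented.** A reader might infer that urinalysis sits at a ceiling in both arms and can show no drug effect. The SAP gives no baseline rate, so that is plausible but unsupported. It also does not carry over to hematology, chemistry, coagulation or lipids.

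5. **Repeat testing.** A reader might infer that the post-dose percentage is inflated because more tests follow dosing. The SAP does not support this. It leaves the schedule to the protocol: "Blood and urine samples for clinical laboratory tests will be collected at timepoints specified in the SoA of the protocol". With equal numbers of tests before and after there is no such effect. With unequal numbers, both arms on the same schedule share it in expectation. A worst-post-dose shift table would not remove it either, since it still takes the extreme over all post-dose tests.

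Finally, the section contradicts nothing and is a workable basic summary. That is a reason to add to it rather than to call it an error.

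**Conclusion.** The point holds for the abnormality count in Section 3.7.2.1. As written, the count cannot separate new from pre-existing abnormalities. If abnormal patients stay abnormal, it understates the drug-placebo difference by the factor (1 − baseline prevalence). Under the assumed 30% and 5% rates, 25 points appears as 17.5, 10 or 2.5 points at 30%, 60% or 90% baseline abnormality. At 5% baseline abnormality the loss is small (23.75 points), so tests that are rarely abnormal at entry are little affected.

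The prevalences, the new-abnormality rates and their persistence are all assumptions; the direction of the effect is not sensitive to the particular rates chosen. No conclusion is drawn about repeat-testing inflation or about an actual urinalysis ceiling. This is a cheap improvement to a primary-endpoint summary, not a flaw that invalidates the plan.

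**What to change.** Keep the planned table and add to Section 3.7.2.1, by treatment:

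- a shift table for each laboratory test, from baseline category (low, normal, high; normal or abnormal for dipstick results) to worst post-dose category, using the Section 3.1.1 baseline;
- a definition of treatment-emergent laboratory abnormality, and its incidence among patients without that abnormality at baseline, with the denominator printed for each arm.

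For tests where most patients are abnormal at baseline, the printed denominator will show how few patients can inform the comparison.

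Cost: one or two standard table shells. No new data collection is needed, since baseline and post-dose values are already planned.

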#### 3.7.2.2 Pregnancy

Pregnancy data will be listed.

### 3.7.3 Immunoglobulins

Total levels of each immunoglobulin (IgA, IgE, IgG, and IgM) from Baseline will be measured at the timepoints specified in the SoA and Schedule of Blood and Urine Sampling of the Protocol.

Values and changes from baseline will be summarized at each scheduled visit and baseline by immunoglobulin. The incidence of positive detection (defined as above normal range; see below) will also be summarized with counts and percentages of patients at the same timepoints.

Immunoglobulin	Normal Range	Positive Detection
IgA	70 – 400 mg/dL (0.7 – 4.0 g/L)	> 400 mg/dL (> 4.0 g/L)
IgE	<= 100 IU/mL	> 100 IU/mL
IgG	700 – 1600 mg/dL (7.0 – 16.0 g/L)	> 1600 mg/dL (> 16.0 g/L)
IgM	40 – 230 mg/dL (0.4 – 2.3 g/L)	> 230 mg/dL (> 2.3 g/L)

All immunoglobulin data will be listed.

#### 3.7.4 Vital Signs

Vital signs will be measured at timepoints specified in the SoA of the protocol. Vital signs will consist of blood pressure, heart rate, respiratory rate, and oral body temperature. Values and changes from baseline will be presented at each scheduled visit and baseline by vital sign. Data will be listed.

#### 3.7.5 Body Weight, Height, and Body Mass Index

Body weight, height, and BMI will be measured/calculated at the timepoints indicated in the SoA of the protocol and the values at Screening will be used to calculate BMI. Data will be listed.

#### 3.7.6 Electrocardiograms

Triplet 12-lead ECG recordings (i.e., 3 useful ECGs without artifacts) will be obtained within approximately 2-5 minutes at each specified timepoint indicated in the SoA of the protocol. The average of the 3 readings will be used to determine ECG intervals and inclusion in summaries. The following ECG parameters will be recorded:

- Heart rate
- PR interval
- QRS interval
- QT interval
- QTc using Fridericia's interval
- RR interval

Values and changes from baseline will be presented at each scheduled visit and baseline by ECG parameter.

All ECGs will be evaluated by a qualified Investigator for the presence of abnormalities. All ECG data will be listed.

#### 3.7.7 Physical Examinations

Targeted physical examinations will be performed at the specified timepoints in the SoA of the protocol (or as clinically indicated). These will be a limited, symptom-directed physical examination only. Conditions noted prior to study drug dosing will be recorded as medical history and those recorded after study drug dosing will be recorded as AEs.

### 3.7.8 *Spleen Examinations*

Spleen evaluations will include ultrasound assessments for splenomegaly at the specified timepoints in the SoA of the protocol and clinical examinations to assess for splenomegaly will be performed at all visits. A clinical examination may also be performed at a clinic visit on Day 35 at the discretion of the study investigator if there are abnormal or clinically significant findings at Day 28.

Splenomegaly is defined as a doubling of the largest dimension of the spleen from baseline or hematologic evidence of splenic sequestration defined as a hematologic abnormality (i.e., anemia, leukopenia, thrombocytopenia) of Grade 3 or greater based on DAIDS criteria.

Counts and percentages of patients with a doubling of the largest dimension of the spleen from baseline will be presented. The largest diameter of the spleen value and changes from baseline will be summarized at each scheduled visit and baseline. All spleen evaluation data will be listed.

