### *3.1.4 Summary Statistics*

Categorical data will generally be summarized with counts and percentages of patients. The denominator used for the percentage calculation will be clearly defined. Continuous data will generally be summarized with descriptive statistics including n (number of non-missing values), mean, median, standard deviation, minimum, and maximum. Geometric mean (GM), and GM CV% will also be provided for PK parameters. The value of zero will be excluded from the calculation of GM and GM CV%.

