## APPENDIX A: LABORATORY TESTS

Samples for the following laboratory tests will be sent to the central laboratory for analysis:

- **Hematology:** Hemoglobin, hematocrit, platelet count, red blood cell (RBC) count, mean corpuscular volume, absolute reticulocyte count, total and differential leucocyte (WBC) absolute count (neutrophils, eosinophils, lymphocytes, monocytes and basophils).
- **Serum chemistry:** Albumin, alkaline phosphatase, alanine aminotransferase, aspartate aminotransferase, C-reactive protein, calcium, chloride, creatinine phosphokinase, gamma-glutamyl transferase, glucose, phosphate, potassium, creatinine, sodium, total bilirubin, total protein, troponin, urea, IL-6 and an immunoglobulin panel (IgA, IgE, IgG and IgM).
- **Coagulation:** activated partial thromboplastin time, prothrombin time
- **Lipids:** High density lipoprotein-cholesterol, low density lipoprotein cholesterol, triglycerides, total cholesterol.
- **Urinalysis and Microscopy** A pre-dose catheter urine specimen will be collected for dipstick analysis of protein, blood, white blood cells, glucose, and pH and microscopy.

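### SAP Section 3.7.8 defines splenomegaly by either of two criteria but plans a patient count for the spleen-size criterion only

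*SAP*

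**What the plan says.** Section 3.7.8 of the SAP gives a two-part definition joined by 'or': "Splenomegaly is defined as a doubling of the largest dimension of the spleen from baseline or hematologic evidence of splenic sequestration". The second part is spelled out as "hematologic evidence of splenic sequestration defined as a hematologic abnormality (i.e., anemia, leukopenia, thrombocytopenia) of Grade 3 or greater based on DAIDS criteria".

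The paragraph that follows sets the outputs. There is one patient count: "Counts and percentages of patients with a doubling of the largest dimension of the spleen from baseline will be presented". There is also a by-visit summary of the largest spleen diameter and its change from baseline, and a listing of all spleen evaluation data.

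Three other places bear on the hematologic part:

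- Section 3.7.2.1 (laboratory tests) sets its counting rule by reference range: "The incidence of abnormalities (as defined by normal ranges", with separate counts before and after the first dose.
- Section 3.7.1 (adverse events) states "Adverse events of special interest include signs and symptoms of a urinary tract infection (UTI) and local vesicular reaction". Splenomegaly is not named there.
- Appendix A shows that the required tests are collected: "Hemoglobin, hematocrit, platelet count, red blood cell (RBC) count, mean corpuscular volume, absolute reticulocyte count, total and differential leucocyte (WBC) absolute count".

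**The concern.** The SAP defines a safety event and then plans to count only part of it. If the plan is followed exactly, a patient whose spleen has not doubled but who develops a Grade 3 or worse cytopenia meets the SAP's definition of splenomegaly and appears in no planned count of it.

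Splenomegaly is not a named endpoint. However, this is a first-in-human study whose primary objective includes safety (Section 2.1.1), and Section 2.2.1 singles out the spleen for repeated ultrasound and for clinical examination at all visits. A reader of the report will look for how many patients had splenomegaly, and the plan supplies a figure for one criterion only.

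A second, smaller gap follows. The size criterion is explicitly a change from baseline; the hematologic criterion is not. The SAP does not say whether a patient already at Grade 3 before dosing qualifies. If the count were assembled later from listings, that rule would be chosen after treatment assignments are known.

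**Working it through.** No formula applies, and the SAP gives no splenomegaly rate to reproduce. The check sets each quantity implied by the definition against each output the SAP text plans.

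| Quantity implied by Section 3.7.8 | Patient count planned in the SAP text? |
|---|---|
| Size criterion (doubling) | Yes, Section 3.7.8 |
| Hematologic criterion (DAIDS Grade 3 or worse cytopenia) | No |
| Splenomegaly as defined (either criterion) | No |

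One of two criteria is counted, and the composite is not.

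Could another section supply the missing counts?

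1. **Laboratory incidence, Section 3.7.2.1.** Abnormality is judged against the normal range. A slightly low hemoglobin and a Grade 3 hemoglobin fall in the same count, so the Grade 3 subset cannot be recovered from it.
2. **By-visit laboratory summaries, Sections 3.7.2.1 and 3.1.4.** Continuous data are shown with "mean, median, standard deviation, minimum, and maximum". A minimum reveals that an extreme value occurred in an arm at a visit. It does not say how many patients crossed a grade threshold, nor whether they also had doubling.
3. **Adverse event tables, Section 3.7.1.** Events are tabulated by preferred term and by maximum severity, but only if reported as adverse events. The section does not tie severity to DAIDS grades.
4. **DAIDS elsewhere.** Outside Section 3.7.8 the term appears only in the list of abbreviations. The grading scale is used in the definition and applied in no planned output.

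The SAP closes this loop for other defined events. Section 3.5 defines biological elimination and recurrence and plans a summary of each. Section 3.7.3 defines positive immunoglobulin detection and plans its incidence.

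Scale only: Section 2.2.4 gives 36 patients randomized 2:1, so 36 × 2/3 = 24 on LBP-EC01 and 36 × 1/3 = 12 on placebo. One uncounted patient would be 1/24 = 4.2% or 1/12 = 8.3% of an arm. These are nominal denominators; the Safety Population by actual treatment may differ. The document gives no basis for predicting how many such patients there will be, and the number may be zero.

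**The case against.** The best defense is that nothing in Section 3.7.8 is false. The planned output is labelled as doubling and reports exactly that. Tabulating only the spleen-specific criterion can also be defended, because a Grade 3 cytopenia may have nothing to do with the spleen. This much stands: the doubling count is right for what it names. What is missing is either the other counts or a sentence saying why they are left out.

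A reader might infer several stronger things that the document does not support:

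- **That the plan reports a wrong splenomegaly rate.** It reports none. The doubling row would mislead only someone who read it as the composite.
- **That the information is lost.** Hematology values and changes are summarized by visit, out-of-range results are counted, and all data are listed. Conditions found at physical examination after dosing are recorded as adverse events (Section 3.7.7), so reported events are tabulated whether or not they are of special interest.
- **That no table will ever show the composite.** The SAP contains no table shells, and Section 8 places detailed programming specifications in a separate document. The supportable statement is that the SAP text plans no such analysis. Which safety events are counted should still be settled in the SAP.
- **That the hematologic criterion has no baseline convention at all.** Section 3.1.1 defines baseline generally, and Section 3.7.2.1 already splits abnormalities at the first dose. Only the patient already at Grade 3 at baseline is left open.

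None of these limits supplies the missing count.

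**Conclusion.** The point holds, as a minor one. The SAP defines splenomegaly by two criteria and plans a patient count for one. The hematologic criterion and the composite have no planned count, and no other section provides one. A patient qualifying on hematology alone would go uncounted under the SAP's own definition, although that patient's values would remain visible in listings and summaries.

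It is minor because no hypothesis is tested (Section 3.1.5), splenomegaly is not a named endpoint, no data are lost, and the number affected may be zero. Confidence is high that definition and output do not match. No claim is made that splenomegaly will in fact be under-reported. The conclusion rests on the SAP text alone; the separate programming specifications have not been seen.

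**What to change.** Before unblinding, reconcile the definition with the output in Section 3.7.8. Section 3.7 already sets the frame: "Safety data will be summarized by actual treatment received (and in total for selected analyses) based on the Safety Population". Within it, present counts and percentages of patients with:

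- (a) splenomegaly as defined, by either criterion;
- (b) doubling alone, as now planned;
- (c) post-baseline anemia, leukopenia or thrombocytopenia of DAIDS Grade 3 or worse, flagging patients already at that grade at baseline.

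State that (c) is derived from the central laboratory values and not from adverse event reports. If the sponsor intends to tabulate size only, the least it should do is say so and give the reason, but the counts above are the better remedy.

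The cost is a few table rows, a short change of wording, and DAIDS grading of hematology that is already collected. The drawback is that the composite may include cytopenias unrelated to the spleen, which is why the components should be shown next to it.
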